### **2.2.1 Subgroup of interest**

Not applicable, no subgroup will be investigated.

## **2.3 Patient disposition, demographics and other baseline characteristics**

Demographic and other baseline data including disease characteristics will be summarized descriptively by treatment group (Cohort 1-3) for the SAF and efficacy analysis set at Week 1.

If major imbalance in relevant demographic or other baseline characteristics are discovered, the study results will be interpreted with more caution and post-hoc supportive analyses may be conducted to adjust for the imbalance.

### **2.3.1 Patient disposition**

Patient disposition displays the absolute and relative frequency of screening failures, the number of patients included in the different analysis sets.

The reasons for screening failure, for missed study visits, for exclusion from analysis populations and for prematurely drop-out are described by frequency tables as well as protocol deviations.

The duration of intervals between study visits are displayed by sample statistics. The interval from screening to first vaccination is analyzed by a frequency table for  $\leq 30$  days versus  $> 30$  days.

---

Not applicable, because all patients received their second dose of study vaccine

## **2.4 Treatments (study treatment, rescue medication, concomitant therapies, compliance)**

### **2.4.1 Study treatment / compliance**

The absolute and relative frequency of performed study visits and performed vaccinations are presented. Sample statistics for the duration of intervals between screening and date of 1st vaccination, date of 1st and 2nd vaccination and date 2nd vaccination to Visit 1/Week 1 are displayed. The interval from the 2nd Vaccination to Visit 1/Week 1, Visit2 /Month 1 and Visit 3/Month 6 are also displayed by sample statistics. Here always the exact date of the respective vaccination is used but not the date of study visit called “Vaccination 1” or “Vaccination 2” which displays the date of phone contact with the patient.

Two types of investigational study drugs are used in this study:

1. Study medication for treatment of MS
2. Study medication for vaccination

The study medication for treatment of MS is displayed by frequencies for type of medication (cohort 3 only), sample statistics for duration of treatment prior to screening (cohort 1 and 3) and frequencies of dose changes, interruptions, or discontinuation until Visit 1, 2, and 3 respectively (cohort1 and 3). For cohort 2 the duration of siponimod interruption (i. e. the time between last dose prior to vaccination and the fist dose after vaccination) is displayed by sample statistics.

The different vaccines are displayed by a frequency table separately for 1st and 2nd vaccination.

### **2.4.2 Prior, concomitant and post therapies**

The number and types of all pretreatments for MS prior to screening are displayed. Here, the current MS-therapy (i. e. starting before screening and ongoing after screening) is not included into counts.

The last disease modifying drug before siponimod (cohort 1 and 2) or the last study medication of cohort 3 is displayed in a frequency table.

Concomitant medications are coded by WHO Drug-dictionary. Frequencies of Anatomic Therapeutical Chemical (ATC) categories and Preferred Names are presented. Here, a medication with multiple entries is counted only once in a ATC category respectively a preferred name category.

## **2.5 Analysis of the primary objective**

### **2.5.1 Primary endpoint**

The **primary clinical question** in this trial is: what is the proportion of SPMS patients treated with siponimod within the three cohorts which mount an immune response to a SARS-CoV-2 modRNA vaccine?

The **primary endpoint** of the study is the proportion of participants achieving seroconversion as defined by detection of SARS-CoV-2 serum functional antibodies one week after second dose of

vaccine in participants treated concomitantly with siponimod and siponimod treatment break (yes/no).

Of note, this is not a randomized trial, therefore no randomization needs to be preserved and the ITT-principle and the associated estimands framework do not apply. However, this protocol will keep as close as appropriate to the terminology and the definitions established within that framework.

The justification for the primary estimand is that it will capture whether siponimod treated participants generate functional antibodies to SARS-CoV-2 vaccine as assessed by geometric mean titers and arithmetic mean for percent inhibition (semiquantitative).

The following attributes describe the primary estimand:

- **Population:** MS patients divided in three cohorts, each receiving a SARS-CoV-2 vaccination as part of clinical routine: (1) vaccination during continued siponimod treatment; (2) vaccination during a siponimod treatment interruption (of approx. 2-3 months); (3) vaccination in MS patients during continued treatment with first-line DMTs or no DMT. Patients who fail to receive their second dose of vaccine for whatever reason will be included in the analysis as non-responders. Patients who did receive their second dose of vaccine and do not have a valid determination of functional antibodies to SARS-CoV-2 for whatever reason will be excluded from the analysis of vaccine efficacy.
- **Variable:** Receiving the second dose of vaccine and achieving seroconversion as defined by detection of SARS-CoV-2 functional antibodies one week after second dose of vaccine (yes/no)
- **Treatment of interest:** siponimod either continuously applied or with a treatment break for the purpose of the vaccination, or first line DMTs or no treatment as part of clinical routine
- **Intercurrent events.** Failure to receive the second dose of vaccine: These patients will be counted as non-responders. Missing or invalid determination of functional antibodies to SARS-CoV-2: These patients will be excluded from the efficacy analyses (if they received their 2nd dose of vaccine)
- **Summary measure:** n.a., there will be no formal comparison between cohorts. Response rates will only be calculated within each cohort.

## 2.5.2 Statistical hypothesis, model, and method of analysis

The efficacy analysis set at Week 1 is used for all analyses of the primary parameter.

The primary analysis will not use any statistical testing or modelling. The absolute numbers and the proportion of participants achieving seroconversion within each cohort will be calculated. It will be augmented by a (descriptive) two-sided 95% confidence interval (exact Clopper-Pearson).

## 2.5.3 Handling of missing values/censoring/discontinuations

Patients who fail to receive their first dose of vaccine for whatever reason are excluded from the efficacy analysis Set(s). The number of these patients is displayed in the patient disposition table.

Patients who fail to receive their second dose of vaccine for whatever reason will be included in the analysis as non-responders. The number of these patients is displayed in the analysis table.

Patients who did receive their second dose of vaccine and do not have a valid determination of functional antibodies to SARS-CoV-2 for whatever reason will be excluded from the analysis of vaccine efficacy. The number of these patients is displayed in the analysis table.

## 2.5.4 Supportive analyses

If relevant differences in demographic or other baseline characteristics are observed post-hoc analysis will be performed to adjust the primary endpoint for these inhomogeneities. A logistic regression model would be applied.

The qualitative and (semi)quantitative antibody results towards coronaviridae are analyzed in addition. The first by frequency tables, the latter by sample statistics.

In several patients the booster vaccination was performed before Visit 3 at Months 6, so that the efficacy results were expected to be influenced by this booster vaccination. Therefore, the analyses of seroconversion in SARS-CoV-2 functional antibodies and reactivity to IFNg and IL-2 SARS-CoV-2 were presented for both subgroup of patient who received / did not receive a booster vaccination before Visit 3 at Month 3.

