1.2 Purpose

MS disease modifying treatments generally target the immune system and may therefore interfere with vaccination responses. The purpose of this study is to understand whether participants can mount an immune response to SARS-CoV-2 modRNA vaccines administered either during continuous siponimod treatment or during a treatment break. Furthermore, the study will investigate the development of anti-SARS-CoV-2 antibody and T-cell titers over six months after participants' vaccination.

2 Objectives and endpoints

Table 2-1 Objectives and related endpoints

Objective(s)	Endpoint(s)
Primary Objective(s)	Endpoint(s) for primary objective(s)

 To estimate the proportion of those achieving seroconversion (i.e. having SARS-CoV-2 serum functional antibodies) after receiving a modRNA vaccine in participants treated concomitantly with siponimod and siponimod treatment break. 	Proportion of participants achieving seroconversion as defined by detection of SARS-CoV-2 serum functional antibodies one week after second dose of vaccine in participants treated concomitantly with siponimod and siponimod treatment break (yes/no)
Secondary Objective(s)	Endpoint(s) for secondary objective(s)

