
 Describing SARS-CoV-2 serum functional antibody levels in participants treated concomitantly with siponimod versus siponimod treatment break versus first-line DMTs and in patients currently not on a DMT Describing the T-cell response to modRNA vaccines in participants treated concomitantly with siponimod versus siponimod treatment break versus first-line DMTs and in patients currently not on a DMT Describing safety, incl. AEs related to discontinuation and new onset of siponimod treatment and patients developing COVID-19 	
 SARS-CoV-2 serum functional antibody levels one week, one month and six months after second dose of vaccine and additionally one month after an optional booster vaccination in participants treated concomitantly with siponimod versus siponimod treatment break versus first-line DMTs and in patients currently not on a DMT SARS-CoV-2 specific T-cell levels one week, one month and six months after second dose of vaccine and additionally one month after an optional booster vaccination in participants treated concomitantly with siponimod versus siponimod treatment break versus first-line DMTs and in patients currently not on a DMT measured by e.g. enzyme-linked immunosorbent spot (ELIspot) assay from peripheral blood mononuclear cells that were stimulated with SARS-CoV-2 peptide mix AEs, SAEs, incl. patients with clinical confirmed COVID-19, events leading to discontinuation in participants treated concomitantly with siponimod versus siponimod treatment break versus first-line DMTs and in patients currently not on a DMT

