8.4 Efficacy

Pharmacodynamic samples will be collected at the time-points defined in the Assessment Schedule (Table 8-1). Follow instructions outlined in the Laboratory manual regarding sample collection, numbering, processing, and shipment.

8.4.1 Efficacy assessment 1

SARS-CoV-2 vaccination efficacy is defined as seroconversion i.e. detection of SARS-CoV-2 serum functional antibodies one week after completion of the vaccination cycle.

8.4.2 Efficacy assessment 2

Additional efficacy assessments are:

- Longitudinal follow-up of SARS-CoV-2 serum functional antibody levels one week, one month and six months after second dose of vaccine and additionally 1 month after a potential booster vaccination
- Longitudinal follow-up of SARS-CoV-2 specific T-cell levels one week, one month and six months after second dose of vaccine and additionally 1 month after a potential booster vaccination

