12.1 Analysis sets

For all analysis sets, participants will be analyzed according to the study treatment(s) received. The safety analysis set will include all participants that received any study drug.

The efficacy analysis sets at one week, one month and six month and additionally after a potential booster vaccination respectively will include all participants who have a valid determination of functional antibodies to SARS-CoV-2 at that time point plus those who failed to receive their second dose of vaccine for whatever reason. The latter will be counted as non-responders. Patients completing vaccination but fail to provide a blood sample at one week after the second vaccination will be excluded from the study and analysis.

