12.4 Analysis of secondary endpoints

All secondary endpoints will be summarized descriptively as frequencies and percentages, or, for continuous data, mean, standard deviation, median, minimum, and maximum will be presented.

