## 2.7 Analysis of secondary efficacy objective(s)

### 2.7.1 Secondary endpoints

The secondary endpoints are analyzed descriptively within each cohort. The efficacy analysis set is used for all analyses of the secondary parameters.

The semiquantitative SARS-CoV-2 serum functional antibody titer (percent inhibition) is summarized by arithmetic mean, standard deviation, minimum, median and maximum by visit. A boxplot graph will be presented.

The SARS-CoV-2 serum functional antibody titer is summarized by geometric mean, geometric coefficient of variation (CV) and 95% confidence intervals for the (geometric) mean. The Visits Screening, Visit 1/Week 1, Visit 2 /Month 1 and Visit3 /Month 6 are displayed separately in this summary table and a boxplot graph with logarithmic y-axis (log base 10).

The same summary table and boxplot will be provided for the following secondary parameters:

- a) Qualitative and quantitative result of IFNg towards SARS-CoV-2 and towards coronaviridae
- b) Qualitative and quantitative result of IL-2 towards SARS-CoV-2 and towards coronaviridae
- c) Combined response in qualitative INFg or IL-s towards SARS-CoV-2 and towards coronaviridae, i. e. reactive to INFg or IL-2 or to both.
- d) Cell viability, CD3 lymphocytes, CD4 and CD8 cells, percentage of CD4+ and CD8+ cell in peripheral blood mononuclear cells

The percent inhibition values for INFg at screening will be displayed for the subset of patients who are reactive at Week 1 versus non-reactive. The same analysis is provided for IL-2.

All other laboratory data (e. g. number of basal/background spots, spots, quality, comments, mutations) are listed only.

The MS activity is measured by relapses. The crude annual relapse rate until end of study and underlying sums (of relapses and patient-years) will be presented.

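### Month-6 antibody and T-cell levels are not split by booster status, and the protocol's one-month post-booster endpoint is neither analysed nor declared dropped in the SAP

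*SAP*

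**What the plan says.** **Booster split.** SAP 2.5.4 notes that a number of patients were boosted before Visit 3 and expects this to influence efficacy results. It responds that "the analyses of seroconversion in SARS-CoV-2 functional antibodies and reactivity to IFNg and IL-2 SARS-CoV-2 were presented for both subgroup", that is, for those boosted and those not boosted before Visit 3.

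**Levels.** SAP 2.7.1 summarises percent inhibition by visit and titre by geometric mean. For titre, "The Visits Screening, Visit 1/Week 1, Visit 2 /Month 1 and Visit3 /Month 6 are displayed separately in this summary table". The same layout is reused for the IFNg and IL-2 results. No booster split is mentioned.

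**Post-booster endpoint.** Protocol Table 2-1 defines the antibody and T-cell level endpoints at one week, one month and six months and "additionally one month after an optional booster vaccination". Protocol 12.1 provides for it: "The efficacy analysis sets at one week, one month and six month and additionally after a potential booster vaccination respectively" are defined. Protocol 12.4 then gives only a general statement for the summaries: "All secondary endpoints will be summarized descriptively as frequencies and percentages", or the usual descriptive statistics for continuous data.

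**SAP basis.** SAP 1 says the SAP follows protocol Amendment 2, which introduced the booster visit. The document history cites the protocol amendment as a reason for the February 2022 update, which added a booster subgroup analysis. SAP 4 declares one departure from the protocol, the change to the efficacy analysis set.

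**The concern.** Protocol 1.2 states that "the study will investigate the development of anti-SARS-CoV-2 antibody and T-cell titers over six months". A Month-6 level that mixes patients with two doses and patients already boosted answers a different question. A level that has held up after two doses and one that has waned and been restored by a booster can give the same mean. The yes/no split does not substitute for a split of levels, because a booster can raise a level without changing a positive result. If the boosted fraction differs between cohorts, their Month-6 levels are also not read on the same basis. Unequal fractions are plausible, since protocol 4.5 foresees that measured responses may inform the booster decision.

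Separately, the protocol added a visit with blood sampling to obtain the one-month post-booster levels. If the SAP neither specifies that summary nor says it was dropped, a reader of the study report cannot tell whether it was forgotten, withheld or judged unnecessary.

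**Working it through.** The plan gives no figure on this point, so there is none to reproduce. The check is a comparison of texts plus simple algebra.

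**1. Where the post-booster time point appears**

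| Place | Post-booster time point |
|---|---|
| Protocol Table 2-1 | Yes, antibody and T-cell levels |
| Protocol 8.4.2 | Yes: "one week, one month and six months after second dose of vaccine and additionally 1 month after a potential booster vaccination" |
| Protocol 12.1 | Yes, an analysis set |
| SAP 1.2 | No; one week, one month and six months only |
| SAP 2.2 | No; a single set keyed to Week 1 |
| SAP 2.7.1, titre | No; four listed visits |
| SAP 2.7.1, percent inhibition | Not specified; summarised by visit without a list |
| SAP 5.3.1 | No; seroconversion at Visits 1 to 3 |
| SAP 4 | Omission not declared |

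SAP 1.2 thus carries 3 of the protocol's 4 time points for each of the two level endpoints. The endpoint table and the titre visit list are the decisive places.

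**2. Which outcomes the split covers.** SAP 2.5.4 does not define reactivity. SAP 2.7.1 c) uses the word for the qualitative result ("i. e. reactive to INFg or IL-2 or to both"), so the quantitative IFNg and IL-2 values are unsplit on the natural reading. Titre and percent inhibition are unsplit on any reading.

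**3. Effect of pooling.** Let a cohort have n patients, m of them boosted before Visit 3, with boosted mean B and unboosted mean U.

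- Pooled mean = [mB + (n − m)U]/n, so pooled mean − U = (m/n)(B − U).
- n = 20 or 22 comes from SAP 3; n = 30 is 20 plus the permitted 10.
- Weight of one boosted patient: 1/20 = 5.0%, 1/22 = 4.5%, 1/30 = 3.3% of (B − U).
- Assumed m = 2, 6 or 10 of 20: 10%, 30% or 50% of (B − U).

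This holds directly for percent inhibition. For titre it holds on the log scale, so the geometric mean is multiplied by R^f, where f = m/n and R is the boosted-to-unboosted ratio of geometric means. Neither is in the documents. With assumed values:

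| f | R = 2 | R = 10 |
|---|---|---|
| 10% | 1.07 | 1.26 |
| 25% | 1.19 | 1.78 |
| 50% | 1.41 | 3.16 |

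**4. Booster samples after Visit 3.** Visit 3 is at week 25–27. A separate booster visit occurs only if more than one week away, so after Visit 3 it starts at week 26–28 at the earliest. It must fall no later than the Month-12 call at week 50–54. The span is 50 − 28 = 22 to 54 − 26 = 28 weeks. SAP 1.1 plans a Month-12 follow-up analysis, but SAP 2.8 mentions only updated adverse-event analyses. Whether these samples are analysed then is not stated.

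**5. Visit 3 standing in for the booster visit.** Taking one month as 4 weeks, a booster given about 3 to 5 weeks before Visit 3 puts the booster visit within one week of Visit 3, and it is not held separately. Pooled Month-6 levels can therefore contain one-month post-booster values.

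**The case against.** The protocol never asks for a booster split at Month 6. The all-patient summary is the protocol endpoint, and the SAP's existing split already goes further than required. On this view, extending it is an enhancement. The split would also not isolate two-dose durability, because the unboosted patients are selected and the boosted group mixes recent with older boosters. The cells may be tiny. Week-1 and Month-1 levels are shown separately, and no formal cohort comparison is planned. The post-booster endpoint is optional and descriptive, and protocol 12.1 and 12.4 still cover it.

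Much of this stands. The all-patient summary is not wrong and should stay. The unboosted group is not an unbiased two-dose estimate. SAP 2.2 and 5.3.1 are weak evidence of omission, since the first names only Week 1 and the second concerns seroconversion. The quantitative T-cell part depends on how reactivity is read. The 1/n weight is only algebra.

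It does not remove the point. The SAP itself gives the reason for splitting, and that reason applies at least as strongly to levels as to yes/no results. The protocol's cover for the post-booster endpoint does not explain why an SAP based on that amendment leaves it out of its endpoint table without saying so.

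**Conclusion.** The concern holds and should be fixed. Two gaps are established from the text: Month-6 levels are pooled over boosted and unboosted patients despite the SAP's own reason for separating them, and the one-month post-booster endpoint is neither implemented nor declared dropped. The handling of booster samples taken after Month 6 is also unstated.

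The actual distortion cannot be derived, because the number boosted and the post-booster levels are not given. What follows from the planned cohort size is a shift of 5% of the boosted-minus-unboosted difference per boosted patient at n = 20. The larger shifts shown rest on assumed counts and ratios. The Week-1 primary endpoint and the Month-6 yes/no outcomes already split are not affected.

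**What to change.** 1. Keep the all-patient Month-6 summary. Add Month-6 titre, percent inhibition and quantitative IFNg and IL-2 by cohort and by booster status before the Visit 3 sample, with the number boosted per cohort. Label these tables post hoc and descriptive, since the last SAP revision followed final data review. Caution that booster status may depend on earlier response.
2. Add a one-month post-booster summary of antibody and T-cell levels by cohort. Flag Visit 3 samples that replace a booster visit, and state that booster visits after Month 6 enter the follow-up analysis. If this summary is not wanted, declare its omission in SAP 4.
3. Tidy the wording. SAP 2.5.4 places Visit 3 at both Month 6 and Month 3. SAP 2.2.1 rules out subgroup analyses, contrary to 2.5.4.

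The cost is a few tables from data already collected and some SAP text. The drawback is small cells. The 95% CI width for a group of k relative to 20, on the log scale for titre with the same SD, is [t(0.975, k − 1)/√k] / [t(0.975, 19)/√20]:

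| k | 18 | 14 | 10 | 6 | 2 |
|---|---|---|---|---|---|
| Relative width | 1.06 | 1.23 | 1.53 | 2.24 | 19.2 |

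For very small cells, show n and individual values instead of an interval.

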## 2.6 Analysis of the key secondary objective

Not applicable, because no key secondary objectives are specified.

## 2.7 Analysis of secondary efficacy objective(s)

### 2.7.1 Secondary endpoints

The secondary endpoints are analyzed descriptively within each cohort. The efficacy analysis set is used for all analyses of the secondary parameters.

The semiquantitative SARS-CoV-2 serum functional antibody titer (percent inhibition) is summarized by arithmetic mean, standard deviation, minimum, median and maximum by visit. A boxplot graph will be presented.

The SARS-CoV-2 serum functional antibody titer is summarized by geometric mean, geometric coefficient of variation (CV) and 95% confidence intervals for the (geometric) mean. The Visits Screening, Visit 1/Week 1, Visit 2 /Month 1 and Visit3 /Month 6 are displayed separately in this summary table and a boxplot graph with logarithmic y-axis (log base 10).

The same summary table and boxplot will be provided for the following secondary parameters:

- a) Qualitative and quantitative result of IFNg towards SARS-CoV-2 and towards coronaviridae
- b) Qualitative and quantitative result of IL-2 towards SARS-CoV-2 and towards coronaviridae
- c) Combined response in qualitative INFg or IL-s towards SARS-CoV-2 and towards coronaviridae, i. e. reactive to INFg or IL-2 or to both.
- d) Cell viability, CD3 lymphocytes, CD4 and CD8 cells, percentage of CD4+ and CD8+ cell in peripheral blood mononuclear cells

The percent inhibition values for INFg at screening will be displayed for the subset of patients who are reactive at Week 1 versus non-reactive. The same analysis is provided for IL-2.

All other laboratory data (e. g. number of basal/background spots, spots, quality, comments, mutations) are listed only.

The MS activity is measured by relapses. The crude annual relapse rate until end of study and underlying sums (of relapses and patient-years) will be presented.

